## 2 Statistical methods

### 2.1 Data analysis general information

The data will be analyzed by Novartis on all patient data after database lock for the respective trial period. It is planned that the data from all centers that participate in this protocol will be used for analysis. Analysis datasets and statistical outputs will be produced using the most recent SAS® Version 9.4 (SAS Institute Inc., Cary, NC, USA), and stored in Novartis global programming & statistical environment (GPS).

Continuous data will be summarized by n, mean, standard deviation (SD), median, first and third quartiles, minimum and maximum. Categorical data will be presented by absolute and relative frequencies (n and %). Summary statistics will also be presented graphically wherever applicable.

If not otherwise specified, p-values and confidence intervals will be two-sided. Unless otherwise stated, the level of significance will be set to 5% (two-sided, family-wise type-I-error).

#### Decimal places

Decimal places will be as follows:

- p-value: 4 decimal places; if p-value is less than 0.0001, display <0.0001.
- Standard error and standard deviation: data precision + 2 decimal places
- Mean, quartile, percentile and median: data precision + 1 decimal place
- Minimum and maximum: same as data precision
- Percentages: 1 decimal place, 0% will be displayed as 0.0 and 100% will be displayed as 100.0.
- Odds ratios and risk ratios will be displayed with two decimal places.
- Confidence interval (CI): data precision + 2 decimal place.

P-values will not be concatenated with “\*” stars in case of significance.

### 2.1.1 General definitions

**Study treatment:** Study treatment refers to:

- Investigational treatment: Secukinumab 150 mg s.c. injection provided in a 1 mL PFS (1 PFS for 150 mg dose).
- Reference treatment: Secukinumab placebo (Placebo) s.c. injection provided in a 1 mL PFS.

Two secukinumab arms will be pooled for the primary analysis and for specified secondary analysis.

**Study treatment start and end date:** Study treatment start date is defined as the first date when study drug is administered and recorded on the Dose Administration Record (DAR) CRF page. Similarly, study drug end date is defined as the last date when a non-zero dose of study drug is administered and recorded on the DAR CRF page.

**Study day:** Study day will be calculated as (event date – study drug start date + 1 day) for the safety analysis and (event date – randomization date + 1 day) for the efficacy analysis. For events prior to study drug start date or randomization date (e.g., an adverse event occurred before the start of first dose), study day will be negative and calculated as (event date – study drug start date) and (event date – randomization date) for safety and efficacy analysis respectively.

#### Screening, baseline and post-baseline definitions

Screening will consist of 2 consecutive visits. During Screening Visit 1, initial assessments will be performed, the duration of the washout period will be determined and Screening Visit 2 will be performed as follows:

- If the washout period is  $\leq 4$  weeks the investigator should proceed directly to Screening Visit 2 on the same day and complete all assessments in the next 4 weeks prior to randomization.
- If the washout period is more than 4 weeks, the patient will be instructed to initiate the necessary washout regimen and return for Screening Visit 2 at 4 weeks prior to randomization.

However in general, screening refers to any procedures (e.g., checking inclusion and exclusion criteria) performed prior to the date of first dose of study treatment (for safety analysis) or prior to the randomization date (for efficacy analysis).

For efficacy analyses, baseline is the last assessment, i.e. the last non-missing observation, (including unscheduled visits) obtained before the randomization. All assessments obtained after randomization are considered as post-baseline unless otherwise specified.

For safety analyses, baseline is the last assessment (including unscheduled visits) obtained on or before the first dose of study treatment (i.e. treatment start date). All assessments obtained after the first dose of study treatment are considered as post-baseline unless otherwise specified.

In general, a baseline value refers to the last measurement made prior to administration of the first dose of study treatment. However, LAB assessments if no pre-treatment value exists, values obtained after first dose of treatment can be used as baseline only if it was collected on the same day as first dose.

**Study completion:** A patient will be considered to have “completed the study” if he/she received a maximum of 20 weeks of study treatment and upon completion of the scheduled study assessments and procedures up to and including the follow up visit (Week 24).

**Study periods:** The study has 3 periods: a screening period consisting of two visits (screening visit 1 and screening visit 2), a treatment period consisting of treatment period 1, treatment period 2, and follow up period of 4 weeks.

**Treatment Period:** There are 2 treatment periods for this study defined as:

Treatment Period 1 is defined as a placebo-controlled, double-blind treatment period starting from baseline till Week 16 pre-dose.

Treatment Period 2 is a double-blinded treatment period starting from Week 16 post-dose till Week 20.

**Lost to follow up:** The patients whose study completion status is unclear because they fail to appear for study visits without stating an intention to withdraw. A patient should not be formally considered lost to follow-up until his/her scheduled end of treatment visit would have occurred.

### 2.1.2 Visit windows

Analysis visit windows will be used for the data that is summarized by visit; they are based on the study evaluation schedule and comprise a set of days around the nominal visit day. For any assessment, there are protocol defined scheduled visits around which analysis visit windows were created to cover the complete range of days within the study. When visit windows are used, all visits will be re-aligned, i.e., they will be mapped into one of the visit windows. E.g., if the *Week 4* visit of a subject is delayed and occurs on Day 46 instead of on Day 29, say, it will be re-aligned to visit window *Week 8*. In the case of major deviations from the visit schedule, or due to unscheduled visits, several assessments of a subject may fall in a particular visit window (either scheduled or unscheduled). Statistical approaches to handle multiple assessments in a given visit window are specified below.

Of note, subjects are allowed to have gaps in visits. All data collected will be displayed in listings.

**Table 2-1 Analysis visit windows**

Analysis Visit	Week	Scheduled Day	Visit Window
Baseline	BSL	1	Up to Day 1*
Week 1	1	8	Day 2-11
Week 2	2	15	Day 12-18
Week 3	3	22	Day 19-25
Week 4	4	29	Day 26-32
Week 5	5	36	Day 33-39
Week 6	6	43	Day 40-46
Week 7	7	50	Day 47-53
Week 8	8	57	Day 54-71
Week 12	12	85	Day 72-99
Week 16	16	113	Day 100-116
Week 17	17	120	Day 117-123
Week 18	18	127	Day 124-130
Week 19	19	134	Day 131-137
Week 20	20	141	Day 138-165

\* Baseline measurement before the first drug administration for safety assessments and before the randomization for efficacy assessments. For efficacy visit windows, refer to date of randomization.

For parameters, which are not collected at every visit, visit windows defined in Table 2-1 will be combined. For example, if a parameter is measured at Week 12 and Week 20 only, Week 12 visit window will extend from Day 2 to Day 99 (combining Week 1 to Week 12 visit windows), Week 24 will extend from Day 100 to Day 165 (combining Week 16 to Week 20).

The mapping described above applies to all visits (not just scheduled visits). Repeat and/or unscheduled visits (which will be numbered in the database according to new NCDS standards) will be mapped for analysis purposes in the same way as scheduled visits. This leaves the possibility, then, for multiple measurements within an analysis window. The following conventions will be used to determine the appropriate measurement to be summarized in the event of multiple measurements within a visit window.

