3.4 Rationale for choice of comparator

The use of early and delayed tapering arms is to evaluate when and how fast NSAIDs can be discontinued after initiating Secukinumab therapy.

A placebo arm up to week 16 is included in this study. Due to the nature of the disease and the outcome measures used (e.g., ASAS20), a placebo arm is necessary to obtain reliable efficacy measurements. This is particularly important as all primary and key secondary endpoints of this trial are based on patient reported outcomes which may be more susceptible to bias in an open label setting. The continuation of the placebo group up to including the week 12 injection can be supported from an ethical standpoint, as patients can continue on a range of concomitant treatments. To obtain unbiased results for the primary endpoint analysis and the blinded evaluation of different time points of initiation of NSAID tapering, it is necessary to switch placebo patients not before all week 16 assessments have been performed and to maintain blinding for the initial treatment group assignment.

Moreover, the inclusion of a placebo group is in accordance with previously implemented methodology and in compliance with the EMA/EMEA (European Medicines Agency) guidelines for clinical trials in AS (EMA 2009).

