**Table 2-2 Rules for flagging values**

Timing of measurement	Type of data	Rule
Baseline	All data	The last measurement made prior to administration of the first dose of study treatment – note this may include measurements taken on the day of randomization (e.g. lab). If a patient did not receive any dose of study treatment then the randomization date will be used.

Timing of measurement	Type of data	Rule
Post-baseline efficacy	All data	
 
• For visits without switch of treatment in the window, the measurement closest to the target will be used. In the event two measurements are taken equally apart (e.g. 1 before target date and 1 after) the first one will be used.
 
• For visits during which the patient switches from placebo to AIN the following will be done:               
 
○ If the analysis visit window is <math>\leq</math> week 16, then:                   
 
▪ If available, the closest measurement to the target date which is ON or BEFORE the switch date will be used (i.e. the closest measurement to target which is on placebo).
 
▪ If there are no data on or before the switch then the closest measurement to the target date after the switch will be used.
 
 
 
○ If the analysis visit window is <math>></math> week 16, then                   
 
▪ If available, the closest measurement to the target date which is AFTER the switch date will be used (i.e. the closest measurement to target which is on AIN).
 
▪ If there are no data AFTER the switch then the closest measurement to the target date before the switch will be used.
 
 
 
 
 

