### **2.7.3 Handling of missing values/censoring/discontinuations**

Missing data for ASAS20 response and other binary efficacy variables (e.g. ASAS5/6, etc.) for data up to Week 20 will be handled as follows:

1. Subjects who drop out of the trial for any reason will be considered non-responders from the time they drop out through Week 20.
2. Subjects who do not have the required data to compute response (e.g. ASAS components) at baseline and at the specific time point will be classified as non-responders.

Patients who were unblinded prior to the scheduled timepoint will be considered non-responders from the time of unblinding up to Week 16. The secondary analysis will use the non-responder imputation only.

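### The Week 16 efficacy window closes at Day 116, so a valid pre-dose Week 16 assessment 4 or more days late is relabelled Week 20 and the patient becomes a Week 16 ASAS20 non-responder (H6)

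*SAP*

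**What the plan says.** SAP 2.1.2 discards the nominal visit label: "all visits will be re-aligned, i.e., they will be mapped into one of the visit windows". Table 2-1 sets the Week 16 row as "Week 16 16 113 Day 100-116", followed by Week 17 from Day 117. Days are counted from randomization: "For efficacy visit windows, refer to date of randomization".

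For parameters not measured at every visit, the rule is: "For parameters, which are not collected at every visit, visit windows defined in Table 2-1 will be combined". The SAP's example is a parameter collected only at Weeks 12 and 20. Its Week 12 window starts at Day 2, and "Week 24 will extend from Day 100 to Day 165 (combining Week 16 to Week 20". The Week 24 label there is evidently a slip for Week 20. In both halves of the example, uncollected weeks go to the next collected visit.

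Protocol Table 6-1 marks patient global assessment, back pain, BASFI and BASDAI at Weeks 12, 16 and 20, and not at Weeks 17-19, which are optional injection visits.

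For binary endpoints, SAP 2.7.3 says that patients without the data needed for response "at baseline and at the specific time point will be classified as non-responders". Table 2-2 chooses among several measurements inside one window. For windows up to Week 16 in which a placebo patient switches, it adds: "If there are no data on or before the switch then the closest measurement to the target date after the switch will be used". A mirror rule applies after Week 16. SAP section 4 lists no changes to the protocol analyses.

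**The concern.** Week 16 is the point at which placebo patients cross over, and it carries two confirmatory hypotheses for the early-tapering arm: H6 (ASAS20) and H11 (BASDAI). Protocol 5.5.4 requires assessments to precede dosing, and SAP 2.1.1 ends Treatment Period 1 at Week 16 pre-dose. A late Week 16 assessment is therefore still valid data on the randomised treatment.

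The upper limit of Day 116 comes from the Week 17 injection visit, at which no efficacy is measured. A patient seen a few days late loses the Week 16 value for a reason unrelated to what was measured. For ASAS20 the consequence is an imputed failure although the true response is known. H6 also gates the rest of the sequence: if it is not rejected, H7-H11 are exploratory only (SAP 2.7.2).

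**Working it through.** **Inputs.** Target days, windows and the combining rule: SAP Table 2-1. Collection schedule: Protocol Table 6-1. Response rates 56.9% and 27.0%, 62 per group, 90% power, two-sided 5%, and the same effect assumed for early tapering at Week 16: SAP section 3. About 190 patients randomised 1:1:1, or 63 per arm. Higher placebo response of 35%: SAP section 3. The share q of Week 16 assessments on Day 117 or later is not in the documents; I assume 0-20%.

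**1. Rebuild the windows for ASAS20 components and BASDAI.**

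| Visit | Target | Window | Days early / late |
|---|---|---|---|
| Week 8 | 57 | 47-71 | 10 / 14 |
| Week 12 | 85 | 72-99 | 13 / 14 |
| Week 16 | 113 | 100-116 | 13 / 3 |
| Week 20 | 141 | 117-165 | 24 / 24 |

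The Week 16/17 midpoint is (113 + 120)/2 = 116.5, which explains Day 116. The midpoint between the collected visits is (113 + 141)/2 = 127.

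**2. Follow one patient.** A pre-dose Week 16 assessment on Day 118 is 118 - 113 = 5 days from its own target and 141 - 118 = 23 days from the Week 20 target. It is filed as Week 20. Table 2-2 cannot recover it, because it selects only within a window. With nothing else in Day 100-116:

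- H6: SAP 2.7.3 makes the patient a Week 16 non-responder.
- H11: the Week 16 BASDAI value is missing in the mixed model. Precision is lost, but no failure is imputed.

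On Table 2-1 alone, Day 118 would be Week 17. Either way it is not Week 16.

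**3. Reproduce the plan's sample size.** With p1 = 0.569, p0 = 0.270, d = 0.299 and mean rate 0.4195:

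n = [1.960 √(2 × 0.4195 × 0.5805) + 1.282 √(0.569 × 0.431 + 0.270 × 0.730)]² / 0.299² = 55.1, or 56 per group without continuity correction.

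With correction, n' = (n/4)[1 + √(1 + 4/(n d))]² = 61.6, or 62 per group. This is the plan's figure, so the corrected formula is used below.

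**4. H6 power when a share q is late, equal across arms.** Both rates are multiplied by (1 - q). Power = Φ{[d - 1/n - 1.960 √(2 p̄(1 - p̄)/n)] / √([p1(1 - p1) + p0(1 - p0)]/n)}, n = 63.

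For q = 0: (0.299 - 0.0159 - 1.960 × 0.0879)/0.0838 = 1.32, giving 90.7%.

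| q | Rates | Difference (points) | Power, placebo 27% | Power, placebo 35% |
|---|---|---|---|---|
| 0% | 56.9 vs 27.0 | 29.9 | 90.7% | 63% |
| 2% | 55.8 vs 26.5 | 29.3 | 89.6% | 61% |
| 5% | 54.1 vs 25.7 | 28.4 | 87.8% | 59% |
| 10% | 51.2 vs 24.3 | 26.9 | 84.4% | 54% |
| 20% | 45.5 vs 21.6 | 23.9 | 76.4% | 46% |

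**5. Unequal lateness.** With 10% late in early tapering only, the difference is 51.2 - 27.0 = 24.2 points. With 10% late in placebo only, it is 56.9 - 24.3 = 32.6 points. The planned difference is 29.9.

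**The case against.** **Size and importance.** No document gives a late-visit rate. At q = 2% the loss is about one point of power. The primary analysis at Week 12 (Day 72-99) and H2-H5 are untouched, and H6 is reached only after H1-H5 are all rejected. All this stands. It limits the importance of the point but does not make the relabelling right.

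**Purpose of the tight limit.** An early upper edge could be meant to keep secukinumab data out of the placebo Week 16 result. That is a fair aim, but a calendar day counted from randomization does not achieve it. The window rejects a Day 118 pre-dose value, yet Table 2-2 allows a post-switch value inside Day 100-116.

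Three stronger readings are tempting and are not supported:

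- *That the rule shrinks the effect in both H6 and H11.* The mixed model for BASDAI does not count a missing value as a failure, so H11 loses precision and its estimate need not shrink. H6 is attenuated only if lateness is similar across arms; step 5 shows that it can also be inflated.
- *That secukinumab data will routinely stand as placebo Week 16, against Protocol 3.4.* That section says "it is necessary to switch placebo patients not before all week 16 assessments have been performed". It governs conduct, whereas Table 2-2 handles data after conduct has deviated. The fallback needs no value from Day 100 to the switch and then one after the switch by Day 116. Assessments precede dosing and the next scheduled efficacy visit is Week 20, so this should be rare.
- *That SF-36 at Week 12 will be filled with Week 4 data.* Forward combining does make that window Day 33-99, but the value closest to target is used. A Day 33 value stands only if none lies nearer Day 85. SF-36 is also outside H1-H11.

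**Conclusion.** The point holds for Week 16. Followed as written, the SAP turns a valid pre-dose assessment on Day 117 or later into a Week 16 ASAS20 non-response for H6 and a missing Week 16 BASDAI value for H11, unless another assessment falls in Day 100-116. The mapping follows from the printed table, its example and the assessment schedule, and is certain apart from the mislabelled Week 24.

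The size is uncertain because it rests on an assumed late share. If that share is equal across arms, H6 loses about 3 points of power at 5% late, 6 at 10% and 14 at 20%, from 90.7%. With 35% placebo response, the starting value is already 63%. If lateness differs by arm, the bias has no fixed direction. The correction should be made before database lock, but it does not threaten the primary result.

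**What to change.** For parameters collected at Weeks 12, 16 and 20, set window limits at the midpoints between collected visits: Week 16 = Day 100-127 and Week 20 = Day 128-165. The late tolerance at Week 16 then becomes 127 - 113 = 14 days, as at Weeks 8 and 12.

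In all three arms, accept as Week 16 only values from Day 100 on that were taken on or before the Week 16 injection. The lower bound keeps Week 12 and earlier records out. Applying the injection condition to every arm avoids accepting a post-injection value under secukinumab while rejecting the same value under placebo. State how patients with no Week 16 injection are handled. Correct the Week 24 label in the example.

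Secondary: delete the two Table 2-2 efficacy fallbacks (a post-switch value standing for Week 16 or earlier, a pre-switch value standing for Week 20) and treat these values as missing. The downside is that a few placebo patients become Week 16 non-responders, which favours secukinumab, so report their number.

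Optional: use midpoint windows for SF-36 and ASAS Health Index at Weeks 4, 12 and 20, that is, splits at (29 + 85)/2 = Day 57 and (85 + 141)/2 = Day 113.

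The cost is SAP wording and a derivation change before lock. No new data are needed.

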**Table 2-2 Rules for flagging values**

Timing of measurement	Type of data	Rule
Baseline	All data	The last measurement made prior to administration of the first dose of study treatment – note this may include measurements taken on the day of randomization (e.g. lab). If a patient did not receive any dose of study treatment then the randomization date will be used.

Timing of measurement	Type of data	Rule
Post-baseline efficacy	All data	
 
• For visits without switch of treatment in the window, the measurement closest to the target will be used. In the event two measurements are taken equally apart (e.g. 1 before target date and 1 after) the first one will be used.
 
• For visits during which the patient switches from placebo to AIN the following will be done:               
 
○ If the analysis visit window is <math>\leq</math> week 16, then:                   
 
▪ If available, the closest measurement to the target date which is ON or BEFORE the switch date will be used (i.e. the closest measurement to target which is on placebo).
 
▪ If there are no data on or before the switch then the closest measurement to the target date after the switch will be used.
 
 
 
○ If the analysis visit window is <math>></math> week 16, then                   
 
▪ If available, the closest measurement to the target date which is AFTER the switch date will be used (i.e. the closest measurement to target which is on AIN).
 
▪ If there are no data AFTER the switch then the closest measurement to the target date before the switch will be used.
 
 
 
 
 

Post-baseline safety	Summary visit information (e.g. lab, ECG, etc.)	
 
• For visits without switch of treatment in the window, the measurement closest to the target will be used. In the event two measurements are taken equally apart (e.g. 1 before target date and 1 after) the first one will be used.
 
• For visits during which the patient switches from placebo to AIN the following will be done:               
 
○ If the analysis visit window is <math>\leq</math> week 16, then:                   
 
▪ If available, the closest measurement to the target date which is ON or BEFORE the switch date will be used (i.e. the closest measurement to target which is on placebo).
 
▪ If there are no data on or before the switch then the closest measurement to the target date after the switch will be used.
 
 
 
○ If the analysis visit window is <math>></math> week 16, then                   
 
▪ If available, the closest measurement to the target date which is AFTER the switch date will be used (i.e. the closest measurement to target which is on AIN).
 
▪ If there are no data AFTER the switch then the closest measurement to the target date before the switch will be used.
 
 
 
 
 

Timing of measurement	Type of data	Rule
Post-baseline safety	Notable abnormalities (e.g. lab)	The most extreme measurement in the window will be used. Note this means a patient can have a notably high and notably low measurement within a window.

## 2.2 Analysis sets

**Randomized set:** The randomized set will be defined as all subjects who were randomized.

**Full analysis set (FAS):** The FAS will be comprised of all subjects from the randomized set to whom study treatment has been assigned. Following the intent-to-treat principle, subjects will be evaluated according to the treatment assigned to at randomization, and in the actual stratum if stratified randomization is used.

**Safety set:** The safety set includes all subjects who took at least one dose of study treatment during the treatment period. Subjects will be evaluated according to treatment received.

